### i. Abbreviations

Abbreviation	Definition
2-HG	2-Hydroxyglutarate
5-FU	5-Flurouracil
a-KG	Alpha-ketoglutarate
AE	Adverse event
AIDS	Acquired immunodeficiency syndrome
ALP	Alkaline phosphatase
ALT	Alanine aminotransferase
AML	Acute myelogenous leukemia
aPTT	Activated partial thromboplastin time
AST	Aspartate aminotransferase
AUC0-12h	Area under the concentration x time curve from Oto 12 h
BCRP	Breast cancer resistance protein
BID	Twice daily
BUN	Blood urea nitrogen
CxDx	Cycle X, Day X
CI	Confidence interval
CIMP	Cytosine-guanine dinucleotide island methylator phenotype
Cmax	Maximum concentration
CpG	Cytosine-guanine dinucleotide
CO2	Carbon dioxide
CR	Complete response
CRA	Clinical Research Associate
CSR	Clinical study report
СТ	Computed tomography
ctDNA	Circulating tumor DNA
СҮР	Cytochrome P450
DDI	Drug-drug interaction
DLT	Dose-limiting toxicity
DME	Drug-metabolizing enzyme

Abbreviation	Definition
DNA	Deoxyribonucleic acid
DOR	Duration of response
ECG	Electrocardiogram
ECHO	Echocardiography
ECOG	Eastern Cooperative Oncology Group
eCRF	Electronic case report form
EDC	Electronic data capture
EQT	End of treatment
GBM	Glioblastoma multiforme
GCP	Good Clinical Practice
GFR	Glomerular filtration rate
GLP	Good Laboratory Practice
HBV,HCV	Hepatitis (B/C) virus
hCG	Human chorionic gonadotropin
HIV	Human immunodeficiency virus
HR	Hazard ratio
IDH, IDHI, IDH2	Isocitrate dehydrogenase protein, 1, 2
IP	Investigational Product
IRB	Institutional Review Board
ІТТ	Intent-to-Treat
LVEF	Left ventricular ejection fraction
MRI	Magnetic resonance imaging
mSV	Millisievert
MTD	Maximum tolerated dose
NCICTCAE	National Cancer Institute Common Terminology Criteria for Adverse Events
NYHA	New York Heart Association
ORR	Objective response rate
OS	Overall survival
PAS	Pharmacokinetic analysis set
PD	Pharmacodynamic
PFS	Progression-free survival

Abbreviation	Definition
PFS6	Progression-free survival at six months
P-gp	P-glycoprotein
PI	Principal Investigator
PK	Pharmacokinetic
PPS	Per protocol set
PR	Partial response
PS	Performance status
QD	Once daily
QTcB, QTcF	Heart-rate corrected QT interval (using Bazett's /Fridericia's formula)
RECIST	Response Evaluation Criteria in Solid Tumors
SAE	Serious adverse event
SAP	Statistical analysis plan
SAS	Safety Analysis Set
SD	Stable disease
	Elimination half-life
TEAE	Treatment-emergent adverse event
TIS	Tumor inflamed signature
TTR	Time to response
ULN	Upper limit of normal

# ii. Protocol Summary

Title	Phase II study of IDHI inhibitor ivosidenib and nivolumab in IDHI mutant gliomas and advanced solid tumors	
Short Title	Phase II of ivosidenib (AG-120) with nivolumab in IDHI mutant tumors	
Protocol Number	HCC 19-096 / CA209-8U3	
Phase	Phase II	
Methodology	Interventional trial comparing response and progression-free survival to historical data	
Methodology	Treatment groups: advanced solid tumor and select gliomas harboring an IDHI mutation	
Estimated Enrollment Period	12 months	
Estimated Study Duration	36 months	
Study Centers	The UPMC Hillman Cancer Center and Memorial Sloan-Kettering Cancer Center	
Primary Objective	
 
To describe the clinical response and six month progression-free survival of patients treated with ivosidenib in combination with nivolumab
 
	
Secondary Objectives	
 
To determine the safety of ivosidenib in combination with nivolumab
 
To summarize longitudinal clinical outcomes of patients treated with ivosidenib in combination with nivolumab
 
	
Exploratory Objective	To evaluate biomaterial-based biomarkers and determine their association with treatment response	

Primary Endpoints	
 
Response
 
Advanced Solid Tumors: Best overall response by RECIST 1.1 as detailed in (Section 11.8) 8 weeks after the initiation of treatment
 
Glioma: Best overall Response by Response Assessment in Neuro-Oncology (RANO), Criteria as detailed in (Section 11.9) 8 weeks after the initiation
 

	
 
of treatment
 
Six Month Progression-Free Survival (PFSG)         
 
All tumor types: Survival to six months after the initiation of treatment without objective tumor progression
 
 
 

Secondary Endpoints	
 
The occurrence of dose-limiting toxicity (DLT), as defined in Section 7.5, in patients receiving ivosidenib plus nivolumab.
 
Adverse Events and Serious Adverse Events related to study treatment (per CTCAE vS.0)
 
Progression-free Survival (PFS) - Survival after the initiation of treatment without objective tumor progression up until 18 months after the last participant has initiated treatment
 

Exploratory Endpoints	
 
Biomarker Studies - quantitative measures of response biomarkers by Nanostring assay (or other available technologies at the time of analysis)
 

Number of Participants	Eighteen in the first stage and seventeen in the second stage, for a maximum of 35 patients
Investigational Product	lvosidenib, Nivolumab, route of administration: intravenous (IV) and oral (po), respectively
Estimated average treatment duration per patient	6 months
Duration of Participation	Up to 2 years
Reference therapies	Ivosidenib or Nivolumab
Statistical Methodology	An optimal Simon two-stage design is employed, where the primary endpoint is a composite of response (RANO for glioma patients or RECIST for solid tumor patients) and PFS6. Dose-limiting toxicity (DLT) is monitored throughout the trial using a Bayesian beta-binomial model. In secondary objectives, adverse events, response over time and progression-free survival are assessed. In exploratory objectives, the relationship between baseline biomarkers and response are described.
Safety Evaluations	Physical examination and ECOG performance status, vital signs, safety laboratory assessments (Hematology, chemistry, thyroid studies, pregnancy test (all women of child-bearing potential [WOCBP]) must have a negative pregnancy test to be eligible. Pregnancy testing to be done every $4 \pm 1$ weeks while on study treatment), AEs.
Data and Safety Monitoring Plan	Investigator/sub-investigators, regulatory, CRS management, clinical research coordinators, clinical research associates, data managers, and clinic staff meet regularly in disease center Data Safety Monitoring Boards (DSMB) to review and discuss study data to include, but not limited to, serious adverse events, participant safety issues, recruitment issues, accrual, protocol deviations, unanticipated problems, breaches of confidentiality Minutes of the disease center DSMB meetings are available to those who are unable to attend in person. A formal, sequential decision rule based on dose-limiting toxicity will be evaluated after every five participants have completed Cycle 1.

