#### 1.4.3.1 Study AG120-C-002

Study AG120-C-002 is evaluating the safety, PK, PD biomarker patterns, and clinical activity of ivosidenib in participants with advanced solid tumors, including cholangiocarcinoma, with an IDHI

mutation. The primary objectives of the study are to assess the safety and tolerability of treatment with ivosidenib administered daily as a single agent dosed orally in participants with advanced solid tumors, including glioma, and to determine the maximum tolerated dose(s) (MTD[s]) and/or the recommended Phase 2 dose(s) of ivosidenib in this population. The initial dosing regimen was 100 mg BID and doses up to 1200 mg once daily (QD) were assessed in a 3+3 dose escalation design; based on the favorable PK profile showing a long elimination half-life ( $t^{1/2}$ ), BID dosing was discontinued after the first cohort and a QD dosing regimen was implemented. The study is divided into a dose escalation phase, followed by an expansion phase to allow for a more robust evaluation of the safety profile and preliminary assessment of clinical activity. This study is currently ongoing.

Efficacy data for Study AG120-C-002 were analyzed separately based on the underlying disease and specific response criteria, including Response Evaluation Criteria in Solid Tumors (RECIST), Response Assessment in Neuro-Oncology (RANO), Response Assessment in Neuro-Oncology for low grade glioma (RANO-LGG): cholangiocarcinoma, chondrosarcoma, or glioma. As of March 10, 2017, 73 participants with cholangiocarcinoma received ivosidenib in the dose escalation and expansion cohorts, with 62 participants receiving ivosidenib at 500 mg QD. Overall, 5% (n=4) experienced a confirmed partial response and 56% (n=41) experienced stable disease.

The 6-month PFS rate was 38.5% and the 12-month PFS rate was 21% (Lowery, Abou-Alfa et al. 2017). As of September 23, 2016, 21 participants with chondrosarcoma had been treated with ivosidenib and 20 were efficacy-evaluable. Eleven (55%) participants experienced stable disease as their best overall response; the remaining participants experienced disease progression (30%) or were not assessed (15%). The 3-month PFS rate was 58% with a median ivosidenib treatment duration of 2.6 months (range, 0 to 24 months) (Tap, et al. 2016).

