### 8.2 Statistical Analysis Plan

# 8.2.1 Primary Objective: Efficacy

Given that the response rate would be expected to be< 10% and PFS < 3.5 months in this patient population of IDHI mutant advanced solid tumors or gliomas, we will consider a participant to have had a positive outcome if they have a positive PFS6 (PFS6 is scored as either No or Yes) *and* they have had at least a partial response (evaluated by RANO in glioma patients and RECIST in patients with solid tumors) at the 12 week scan.

An Optimal Simon two-stage design is employed, where a probability of positive outcome less than 0.1 would not be promising and a probability of positive outcome 0.3 would warrant further interest. In the first stage, 18 participants will be accrued. If three or more participants have positive outcomes, 17 more participants will be accrued. If 7 or more out of the 35 participants have positive outcomes, the null hypothesis p<0.1 will be rejected at a=0.05. This design has 90% power if p > 0.3.

For all tumor types, six-month progression-free survival (PFS6) is defined as survival to six months after the initiation of treatment without objective tumor progression

The probability of positive outcome and 95% confidence interval will be estimated using the method of Koyama and Chen (Koyama and Chen 2008).

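### The primary composite counts response at one early scan only, so a participant with a first partial response at week 16 or 24 who is progression-free at six months is scored a failure

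*Combined protocol and SAP*

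**What the plan says.** Section 8.2.1 scores a participant as positive only if PFS6 is met and there is "at least a partial response (evaluated by RANO in glioma patients and RECIST in patients with solid tumors) at the 12 week scan". The Protocol Summary and section 2.2.1 call the response endpoint best overall response but fix it at 8 weeks for both tumour groups; for glioma the Summary refers to the criteria in "Section 11.9) 8 weeks after the initiation" of treatment. Section 8.1.2 places the first radiographic assessment at week 12.

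Sections 3.1 and 6.5.1 schedule scans every 8 weeks (±7 days) from the first day of treatment. PFS6 is read at six months.

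The design in 8.2.1 takes the view that "a probability of positive outcome less than 0.1 would not be promising" and that "a probability of positive outcome 0.3 would warrant further interest". It continues with 3 or more positives among 18 and declares success with 7 or more among 35. The historical figures are overall or best response rates: section 1.2.1 lists response rates from checkpoint-inhibitor trials, and section 1.4.3.1 reports for ivosidenib in cholangiocarcinoma that "Overall, 5% (n=4) experienced a confirmed partial response".

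The Summary adds that "In secondary objectives, adverse events, response over time and progression-free survival are assessed". Sections 2.2.2 and 8.2.3 do not carry response over time any further.

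**The concern.** The composite is meant to find participants who both respond and stay progression-free for six months. A participant whose PR is first seen at week 16 or 24, and who has not progressed at month 6, has done both, yet the rule as written scores that participant negative. No success can be declared before month 6 anyway, so the later scans are available by the time success is judged.

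Three things in the documents pull against a single early reading:

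- the label best overall response, which one post-baseline scan cannot deliver;
- the historical comparators, which are not tied to one early scan;
- for glioma, an appendix definition of PR that one scan cannot satisfy.

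At stake are the counted success rate, the chance of stopping after 18 participants, and the match between what is counted and what it is compared with.

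**Working it through.** **1. Which scans can count.** Scheduled scans before month 6 fall at about weeks 8, 16 and 24. The latest date for the third is 24 × 7 + 7 = 175 days, inside six months. Only the week-8 scan falls at or before either stated time (8 or 12 weeks), and no scan is scheduled at week 12. So under either text a first PR at week 16 or 24 does not count.

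**2. Glioma.** Table 11.9.1 requires a PR to be sustained for at least 4 weeks. Table 8 requires PR at consecutive assessments at least 4 weeks apart. On an 8-weekly schedule the scan after week 8 is week 16, so a best overall PR cannot be established at week 8.

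**3. The plan's own figures.** Inputs from 8.2.1: n1 = 18, continue if X1 ≥ 3; n = 35, reject if the total ≥ 7; p0 = 0.1; p1 = 0.3. The plan states that "the null hypothesis p<0.1 will be rejected at a=0.05" and that "This design has 90% power if p > 0.3".

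P(reject | p) = Σ over x = 3 to 18 of b(x; 18, p) × P(Bin(17, p) ≥ 7 − x)

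- p = 0.1: 0.0474. p = 0.3: 0.9016. Both agree with the plan.
- Stage-1 stop, P(X1 ≤ 2): 0.734 at p = 0.1. At p = 0.3 it is 0.0016 + 0.0126 + 0.0458 = 0.060.
- A search over designs with alpha ≤ 0.05 and power ≥ 0.90 returns this same design as Simon optimal.

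**4. Effect of the early cut-off.** Suppose 0.30 is the rate of PR by month 6 plus PFS6, and a share f of those participants first respond after the scored scan. The counted rate is 0.30 × (1 − f). The documents give no value for f, so the range is assumed.

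| f (assumed) | Counted rate | Power | Stage-1 stop |
|---|---|---|---|
| 0% | 0.30 | 0.902 | 0.060 |
| 10% | 0.27 | 0.828 | 0.099 |
| 20% | 0.24 | 0.718 | 0.157 |
| 30% | 0.21 | 0.571 | 0.238 |

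**5. Direction of the error.** If the month-6 composite rate is 0.10, the counted rate is 0.09, 0.08 or 0.07 for f = 10%, 20% or 30%, and the rejection probability is 0.029, 0.016 or 0.008 instead of 0.047. The rule is conservative.

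**6. The other reading of 0.30.** If 0.30 is the rate at the early scan, the month-6 rate is 0.30/(1 − f): 0.333 for f = 10% and 0.375 for f = 20%. Counting later responses then raises power from 0.902 to 0.951 or 0.981.

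**The case against.** **The plan's power is right as stated.** The 90% is given for a 0.30 rate of the composite as defined, scan time included, and it reproduces. A reader might infer that the trial is underpowered against its own claim. The documents do not support that: the loss in step 4 appears only if 0.30 is taken as the month-6 rate. This objection stands.

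**The early scan does buy something.** A reader might infer that the cut-off saves no time at all. Because the composite joins its halves with *and*, a non-responder at the scored scan is already a failure, so 16 of 18 without a PR settles stage 1 before month 6. With an early PR rate of 0.05, 0.08 or 0.10, P(X1 ≤ 2) is 0.94, 0.83 or 0.73. The plan neither states nor uses this advantage, and a decision to continue still needs month-6 data, but the advantage is real.

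**Evidence for late first responses is thin.** Section 5.5.2 on treatment beyond progression, and the mention of an extended response in 6.6.1, might be taken as the protocol expecting them. Section 5.5.2 concerns benefit after progression, and such participants would normally fail PFS6. Extended most naturally means lasting. Neither passage supplies a late-responder share.

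**The mismatch with p0 has a second source.** Requiring PFS6 as well makes the composite stricter than any cited response rate, whichever scan is used. Moving the scan window does not remove that part.

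**Late responses are not wholly ignored.** The Summary does promise response over time. What is missing is the detail in 2.2.2 and 8.2.3.

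**Early PR plus PFS6 is a coherent landmark endpoint.** A PR first seen at week 24 has little observed durability, and three looks give more chances of a PR from measurement error than one. This is a fair argument for choosing the early scan deliberately. The plan does not make it, and the label best overall response points the other way.

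**Conclusion.** The concern holds as a misclassification in the endpoint as written. A first PR at week 16 or 24 with PFS6 is scored a failure under either stated week, and the glioma reading conflicts with the protocol's own response criteria. Both follow from the text without any assumption.

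The size does rest on assumptions. If 0.30 is the rate of response by month 6 plus PFS6, and 10% to 30% of those participants first respond after the scored scan, power falls from 0.90 to between 0.83 and 0.57, and the stage-1 stop probability rises from 0.06 to between 0.10 and 0.24.

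It would be wrong to conclude that the 90% figure is an error or that a positive result would be unsafe. The arithmetic is right, and the effect runs against the combination without inflating type I error. This is an inexpensive improvement worth making, not a defect that invalidates the design.

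**What to change.** In the Protocol Summary and sections 2.2.1, 8.1.2 and 8.2.1:

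- Reconcile the 8-week and 12-week texts with the 8-weekly scan schedule.
- Define the response half as CR or PR by RECIST or RANO, first documented at any scheduled scan from first restaging through the six-month PFS6 assessment and before progression.
- For glioma, state that a PR first seen by month 6 counts if confirmed at the next scheduled scan at least 4 weeks later, even if that scan falls after month 6. A PR first seen at week 24 would be confirmed at about week 32.
- Report the time of first response, and keep response at the first scan as a supportive summary. Put both into 2.2.2 and 8.2.3, which supplies the response-over-time item in the Summary.

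Keep 18 and 35, the cut-offs 3 and 7, and p0 = 0.1. The composite is a subset of response, which 8.2.1 already expects to be below 10%, so alpha at p0 = 0.1 remains 0.047.

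The change needs no extra participants or scheduled scans. Its costs are a slightly easier success definition with more looks for a PR, some stage-1 futility stops that become certain later than the first scan, and a few glioma responses that wait one further scheduled scan for confirmation.

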### 1.0 Introduction and Study Rationale

### 1.1 The T-Cell InflamedMicroenvironment

The T cell-inflamed tumor microenvironment has been described as a potential predictive biomarker for response to multiple immunotherapies including therapeutic vaccines, anti-cytotoxic T-lymphocyte-associated protein (CTLA}-4, and anti-programmed cell death protein 1 (PD-1}/PD-1 ligand 1 (PD-LI} antibodies (Harlin, Meng et al. 2009, Gajewski, Louahed et al. 2010, Ji, Chasalow et al. 2012, Topalian, Hodi et al. 2012, Gajewski, Woo et al. 2013, Spranger, Spaapen et al. 2013). Analysis of the tumor microenvironment in patients with melanoma suggests that approximately 35-50% of cases show evidence of spontaneous priming of anti-tumor T cells, leading to migration of CD8+ effector T cells into

tumor sites. This phenotype has been designated the T cell-inflamed tumor microenvironment and is characterized by expression of T cell markers, chemokines for T cell recruitment, and transcripts indicative of type I interferon (IFN) signaling (Harlin, Meng et al. 2009, Gajewski, Louahed et al. 2010, Gajewski, Woo et al. 2013} (Figure 1].

This phenotype may be most robustly predicted using gene expression profiling, which in addition to response prediction, may also potentially be useful in identifying those that will not respond. Patients harboring noninflamed tumors may require treatment strategies which

modulate the immune response to facilitate the influx of tumor infiltrating lymphocytes (TIL) and conversion from a non-inflamed to an inflamed tumor.

We have recently expanded this analysis of the T cell-inflamed tumor microenvironment to all tumor types via analysis of The Cancer Genome Atlas (TCGA) identifying subsets of inflamed and non-inflamed tumors across all histologies (Spranger, Luke et al. 2016) (Figure 2).

Additionally, our group was the first to identify tumor-intrinsic oncogene signaling pathways mediating immune exclusion and resistance to cancer immunotherapy. In a disease-specific fashion, we have identified WNT/-catenin signaling (Spranger, Bao et al. 2015) and phosphatase and tensin homolog (PTEN) loss in melanoma as well as fibroblast growth factor receptor 3 (FGFR3) activation in urothelial bladder cancer (Sweis, Spranger et al. 2016). To more broadly assess the impact of oncogene signaling

1 pathways on immune exclusion, we recently separated all solid tumors of TCGA into T cell-inflamed and

2 non-T cell-inflamed and looked for somatic alterations associated with the non-T cell-inflamed

3 phenotype. Utilizing a cut off of at least a 10-sample difference for mutations between non-T cell-

4 inflamed and T cell-inflamed, we identified isocitrate dehydrogenase 1 (IDHI) as having the most

5 powerful association with non-inflamed tumors (while IDH2 also showed a less powerful association,

Figure 3).

14

9 These IDHI alterations were present across tumor histologies with the vast majority being identified as 10 R132H and minority of R132C (**Figure 4**). While glioma was the most highly represented tumor type 11 others included breast cancer, cholangiocarcinoma, melanoma and other tumor types described 12 previously to harbor IDHI alterations. This suggests that IDHI alterations may have a pan-cancer effect 13 in driving immune exclusion.

# 15 **1.2 Study Rationale**

16 While PDI-blocking immunotherapy has rapidly changed the landscape of cancer treatment, most

17 patients do not benefit from this therapy. This is particularly evident for certain cancers that generally

18 display the non-T cell-inflamed tumor microenvironment: gliomas, breast cancers and gastrointestinal

19 cancers such as cholangiocarcinomas, among others. Our data suggest that aberrant IDH activity may

20 play a role in in limiting the efficacy of immunotherapy and data from other groups appear to

21 collaborate this finding. A previous study (Kohanbash, Carrera et al. 2017) described a role for mutant

22 IDH in mediating immune exclusion in human glioma samples and recapitulated this effect in an IDH

mutant syngeneic mouse model. Mutations in IDH confer gain-of-function activity by converting aketoglutarate to the oncometabolite R-2-hydroxyglutarate, which coordinates epigenetic changes that promote malignant transformation (Dang, White et al. 2009).

Gene expression profiling of gliomas revealed reduced expression of T cell-associated genes and IFN-yinducible cytokines in the IDH-mutated gliomas compared to gliomas with wild-type IDH. Mice possessing gliomas with mutated IDH recapitulated the immunophenotype of human IDH-mutated gliomas and demonstrated poor CD8 T cell infiltration. R-2-hydroxyglutarate limited intra-tumoral production of chemokines CXCL9 and CXCLI0, resulting in decreased T cell recruitment into IDHmutated gliomas (Kohanbash, Carrera et al. 2017).

Finally, a selective inhibitor that blocks the ability of mutated IDH-1 to produce the oncometabolite R-2hydroxyglutarate restored chemokine expression, promoted T cell infiltration, and increased the efficacy of therapeutic peptide vaccination against gliomas **(Figure S)** (Dang, White et al. 2009).

Thus, inhibitors of mutant IDH are potential therapeutic candidates to reverse immune evasion in gliomas and potentially other tumor types. Collectively, these data indicate that it might be possible to therapeutically target mutant IDH1 within a non-inflamed tumor to re-engage anti-tumor immune defenses and potentially drive combinatorial benefit with anti-PD1 immunotherapy.

Ivosidenib is a novel, first-in-class compound targeted selectively to inhibit the mutated IDH1 enzyme. Small molecule inhibition of the mutant IDH enzyme represents a novel, targeted approach to cancer treatment. Direct inhibition of the gain-of-function activity of the IDH1 mutated protein is intended to inhibit the production of the oncogenic metabolite 2-HG. Ivosidenib has been extensively evaluated in nonclinical studies and has been shown in vitro and in vivo to effectively inhibit the gain-of-function activity of the mutated protein leading to> 95% inhibition of the production of the potential oncometabolite 2-HG. In clinical studies, up to 98% inhibition of plasma 2-HG has been observed in participants with solid tumors after QD dosing of ivosidenib.

Here, we propose a Phase II study of the IDH1 inhibitor ivosidenib and nivolumab in IDH1 mutant gliomas and advanced solid tumors to assess toxicity and assess the preliminary activity of this combination regimen. We hypothesize that safe doses will be observed for ivosidenib with nivolumab

and that a higher overall response rate and improved progression free survival relative to historical controls will be seen. Within this study we will integrate detailed immune monitoring, genomic profiling of the tumor, and systemic immune response. This study will lay the groundwork for potential subsequent randomized studies and has the potential to improve outcomes for a high-need patient population through expanding the utility of cancer immunotherapy.

